19. **Cycle 1:** Serial, 3-mL blood samples will be taken for determination of plasma CPX-POM and metabolites concentrations during Cycle 1 at 0.25, 0.5, 1.0, 1.5, 2.0, 3.0, 4.0, 5.0, 6.0, 8.0, 10.0, 12.0, and 24.0 hours following completion of the 10-minute IV infusion on Day 1 and on Day 5. Each PK sample should be collected as close as possible to the planned time. The 12.0 hour collection can have a +/- 1-hour window (collect within 11 to 13 hours) and the exact time must be recorded. The actual date and time of each blood sample collection will be accurately recorded.
20. **Cycle 1:** Complete 24-hour urine samples for determination of CPX-POM and metabolites concentrations, and measurement of urine volume will be obtained from each patient in urine collection and storage containers during Cycle 1. A sample will be taken at pre-dose on Day 1, and complete urine samples will be collected at 0-12 and 12-24 hour collection intervals post-dose on Days 1 and 5. The 12 hour collection can have a +/- 1-hour window (collect within 11 to 13 hours) and the exact time must be recorded.
21. **Cycle 1:** Urine β -glucuronidase activity will be determined in the complete 24-hour urine samples collected on Day 1 and Day 5 of Cycle 1.
22. 7-mL blood samples will be obtained in EDTA-containing blood collection tubes at pre-dose on Day 1 and Day 5 of each treatment cycle, and on Day 22 of the last treatment cycle. Plasma and buffy coat (PBMCs) will be isolated, transferred to storage tubes, and stored frozen.
23. BSA will be calculated by the site personnel using the Dubois method of calculation using screening height and baseline weight measurements. BSA is to be recalculated before study drug administration on Day 1 of every other treatment cycle, starting with Cycle 3 and the patient's study drug dose adjusted accordingly.
24. CPX-POM infusions will be administered once every 24 hours as 10-minute IV infusions on Days 1-5 of each 21-day treatment cycle. After completion of Cycle 1 for the first 4 to 6 patients, the SRC will review safety, PK, and PD data to determine if any changes to the dosing schedule are indicated (e.g., adding an additional 5 days of dosing to each treatment cycle).

GLOSSARY OF ABBREVIATIONS AND DEFINITION OF TERMS

| | |
|----------------------|---|
| AE | adverse event |
| ALT | alanine aminotransferase |
| ANC | absolute neutrophil count |
| aPTT | activated partial thromboplastin time |
| AST | aspartate aminotransferase |

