6.1.4. Dosage and Administration

CPX-POM will be administered as an IV infusion once daily on Days 1-5 of each 21-day treatment cycle. CPX-POM will be added to a 100 mL piggyback bag of 0.9% sodium chloride solution and infused over a 10-minute period. The initial dose for the first patient enrolled (i.e., Cohort 1) will be 30 mg/m².

At baseline, the body surface area (BSA) will be calculated by the Dubois method using Screening height and baseline weight measurements. The baseline BSA is to be used to determine the patient's study drug dose. Thereafter, BSA is to be recalculated on Day 1 of every other treatment cycle, starting with Cycle 3, and the patient's study drug dose adjusted accordingly.

$$\text{Dubois Formula: } \text{BSA} = 0.007184 \times W^{0.425} \times H^{0.725}$$

The dose escalation procedure is described in Section 4, and further details and example doses are shown in Section 4.2.

After completion of Cycle 1 for the first 4 to 6 patients, the SRC will review safety, PK, and PD data to determine if any changes to the dosing schedule are indicated (e.g., adding an additional 5 days of dosing to each treatment cycle).

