[c] The denominator is the number of females in each dose group.

[d] Body Surface Area (BSA) (kgxm) = 0.007184 x Weight (kg)^{0.425} / (Height (m))^{0.725} (Dubois formula).

Program: (Program name.sas) (run on: DDMMYYYY HH:MM)

Filename: (Specify file name.rtf)

Sponsor: CicloMed
Protocol: CPX-POM-001
Statistical Analysis Plan
(TFL shells):
Version 1.0 / 02FEB2018

Table 14.1-4 - Protocol Deviations
 (Safety Population)

Protocol Deviations Category	CPX-POM 30 mg/m ² N=1 n (%)	CPX-POM [D2] mg/m ² N=X n (%)	CPX-POM [D3] mg/m ² N=X n (%)	CPX-POM [D4] mg/m ² N=X n (%)	CPX-POM [D5] mg/m ² N=X n (%)	CPX-POM [D6] mg/m ² N=X n (%)	CPX-POM [D7] mg/m ² N=X n (%)
Any Protocol Deviations	XX (XX.X)	XX (XX.X)	XX(XX.X)	XX (XX.X)	XX(XX.X)	XX(XX.X)	XX(XX.X)
Inclusion / Exclusion Criteria INCL01 <cont.>	XX (XX.X)	XX (XX.X)	XX(XX.X)	XX (XX.X)	XX(XX.X)	XX(XX.X)	XX(XX.X)
Prohibited Medications	XX (XX.X)	XX (XX.X)	XX(XX.X)	XX (XX.X)	XX(XX.X)	XX(XX.X)	XX(XX.X)

<cont.>

A patient could be counted under more than one category.

Program: (Program name.sas) (run on: DDMMYYYY HH:MM)

Filename: (Specify file name.rtf)

PROGRAMMING NOTES:

- Categories are from the protocol deviations criteria form, the table only shows examples.

Sponsor: CicloMed
Protocol: CPX-POM-001
Statistical Analysis Plan
(TFL shells):
Version 1.0 / 02FEB2018

Protocol: CPX-POM-001

--- DELIVERY TYPE ---

Page 1 of 2

Table 14.1-5.1 - Disease Characteristics
(Safety Population)

	CPX-POM 30 mg/m ² N=1	CPX-POM [D2] mg/m ² N=X	CPX-POM [D3] mg/m ² N=X	CPX-POM [D4] mg/m ² N=X	CPX-POM [D5] mg/m ² N=X	CPX-POM [D6] mg/m ² N=X	CPX-POM [D7] mg/m ² N=X
Cancer Type? [n (%)]							
Solid Tumor	XX (XX.X)	XX (XX.X)	XX (XX.X)	XX (XX.X)	XX (XX.X)	XX (XX.X)	XX (XX.X)
Lymphoma	XX (XX.X)	XX (XX.X)	XX (XX.X)	XX (XX.X)	XX (XX.X)	XX (XX.X)	XX (XX.X)
Other	XX (XX.X)	XX (XX.X)	XX (XX.X)	XX (XX.X)	XX (XX.X)	XX (XX.X)	XX (XX.X)
Solid Tumor Organ Site [n (%)]							
Lung	XX (XX.X)	XX (XX.X)	XX (XX.X)	XX (XX.X)	XX (XX.X)	XX (XX.X)	XX (XX.X)
Breast	XX (XX.X)	XX (XX.X)	XX (XX.X)	XX (XX.X)	XX (XX.X)	XX (XX.X)	XX (XX.X)
Colon	XX (XX.X)	XX (XX.X)	XX (XX.X)	XX (XX.X)	XX (XX.X)	XX (XX.X)	XX (XX.X)
Prostate	XX (XX.X)	XX (XX.X)	XX (XX.X)	XX (XX.X)	XX (XX.X)	XX (XX.X)	XX (XX.X)
Other	XX (XX.X)	XX (XX.X)	XX (XX.X)	XX (XX.X)	XX (XX.X)	XX (XX.X)	XX (XX.X)
Time since first diagnosis of Cancer (months)							
n	XX	XX	XX	XX	XX	XX	XX
Mean	XX.X	XX.X	XX.X	XX.X	XX.X	XX.X	XX.X
SD	XX.XX	XX.XX	XX.XX	XX.XX	XX.XX	XX.XX	XX.XX
Minimum	XX	XX	XX	XX	XX	XX	XX

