Table 14.1-6.1.2 - Concomitant Medications by Therapeutic Class and Preferred Term
(Safety Population)

Replicate of Table 14.1-6.1.1

PROGRAMMING NOTES:

- Update footnote: replace 'A prior medication is a medication whose end date is before the date of first CPX-POM dose' by 'A concomitant medication is a medication that started before the date of first dose and stopped on (or is ongoing after) the date of first dose OR a medication whose start date is either the same as (or after) the date of first dose'.
- Update 'At least one prior medication' by 'At least one concomitant medication'.
- The Therapeutic Classes are presented by alphabetical order and the Preferred Terms are sorted within Therapeutic Classes by alphabetical order.
- A medication / therapy can appear within more than one Therapeutic Class.

Table 14.1-7 - Overall Exposure to Study Drug and Drug Compliance
 (Safety Population)

	CPX-POM 30 mg/m ² N=1	CPX-POM [D2] mg/m ² N=X	CPX-POM [D3] mg/m ² N=X	CPX-POM [D4] mg/m ² N=X	CPX-POM [D5] mg/m ² N=X	CPX-POM [D6] mg/m ² N=X	CPX-POM [D7] mg/m ² N=X
Study Drug Exposure (days) [a]							
n	XX	XX	XX	XX	XX	XX	XX
Mean	XX.X	XX.X	XX.X	XX.X	XX.X	XX.X	XX.X
SD	XX.XX	XX.XX	XX.XX	XX.XX	XX.XX	XX.XX	XX.XX
Minimum	XX	XX	XX	XX	XX	XX	XX
Median	XX.X	XX.X	XX.X	XX.X	XX.X	XX.X	XX.X
Maximum	XX	XX	XX	XX	XX	XX	XX
Study Drug Exposure (mg) [b]							
n	XX	XX	XX	XX	XX	XX	XX
Mean	XX.X	XX.X	XX.X	XX.X	XX.X	XX.X	XX.X
SD	XX.XX	XX.XX	XX.XX	XX.XX	XX.XX	XX.XX	XX.XX
Minimum	XX	XX	XX	XX	XX	XX	XX
Median	XX.X	XX.X	XX.X	XX.X	XX.X	XX.X	XX.X
Maximum	XX	XX	XX	XX	XX	XX	XX

[a] The CPX-POM exposure expressed in days is defined as the number of days between the first dose taken date and the last dose taken date + 1 day.

[b] The CPX-POM exposure expressed in mg is defined as: dose per m² x Body Surface Area x CPX-POM exposure expressed in days.

Program: (Program name.sas) (run on: DDMMYYYY HH:MM)

Filename: (Specify file name.rtf)

Sponsor: CicloMed
Protocol: CPX-POM-001
Statistical Analysis Plan
(TFL shells):
Version 1.0 / 02FEB2018

Protocol: CPX-POM-001

--- DELIVERY TYPE ----

Page 1 of 2

Table 14.2.1 - Patients who have had at least one other post-baseline tumor assessment
(Efficacy Population)

	CPX-POM 30 mg/m ² N=1	CPX-POM [D2] mg/m ² N=X	CPX-POM [D3] mg/m ² N=X	CPX-POM [D4] mg/m ² N=X	CPX-POM [D5] mg/m ² N=X	CPX-POM [D6] mg/m ² N=X	CPX-POM [D7] mg/m ² N=X
At least one other post-baseline tumor assessment	XX (XX.X)	XX (XX.X)	XX (XX.X)	XX (XX.X)	XX (XX.X)	XX (XX.X)	XX (XX.X)

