Protocol: CPX-POM-001
Statistical Analysis Plan
(TFL shells):
Version 1.0 / 02FEB2018

Protocol: CPX-POM-001

--- DELIVERY TYPE ---

Page 1 of X

Listing 16.1.7-1 - Treatment Administration
 (All Patients)

Center/ Patient	Visit	CPX-POM Dose group	CPX-POM Dose Amount per Prot.?	If no, Reason for Adjustment?	Total Inf. Bag vol. of Sal. and CPX-POM (ml)	Was Total Vol. Inf.?	If no, actual Vol. Inf.?	Adm. Date (Day) Inf. Start Time- Inf. End Time	Arm Used for IV	Infusion Interrupted?
XXXXXXXX	BAS	30 mg/m ²	Yes		XXX	Yes		DDMMYYYY (XX) HH:MM-HH:MM	Right	
	C1 TRT D2	30 mg/m ²	Yes		Yes	Yes		DDMMYYYY (XX) HH:MM-HH:MM	Right	
	C1 TRT D3	30 mg/m ²	Yes		XXX	Yes		DDMMYYYY (XX) HH:MM-HH:MM	Right	
	C1 TRT D4	30 mg/m ²	Yes		XXX	Yes		DDMMYYYY (XX) HH:MM-HH:MM	Right	
	C1 TRT D5	30 mg/m ²	No	Adverse event	XXX	No	XXX	DDMMYYYY (XX) HH:MM-HH:MM	Right	Yes [a]

<repeat for Days 1,2,3,4 and 5 of next cycles if relevant>

Prot.: Protocol; Inf.: Infusion/Infused; Vol.: Volume; Sal.: Saline; Adm.: Administration; Inter.: Interruption/Interrupted;
 IV: Intravenous

[a]: see further details regarding the infusion interruption in Listing 16.1.7-2

Program: (Program name.sas) (run on: DDMMYYYY HH:MM)

Filename: (Specify file name.rtf)

PROGRAMMING NOTES:

- Listing to be sorted by increasing CPX-POM dose.

Sponsor: CicloMed
Protocol: CPX-POM-001
Statistical Analysis Plan
(TFL shells):
Version 1.0 / 02FEB2018

Protocol: CPX-POM-001

--- DELIVERY TYPE ---

Page 1 of X

Listing 16.1.7-2 - Infusion Interruption
 (All Patients)

Center/ Patient	Visit	CPX-POM Dose group	Reason for Inf. Inter.?	Specify	Adm. Date (Day) Time Inf. Inter.	Inf. Rest.?	Time Inf. Restarted	Reason for Not Restarting?	Specify	Inf. Site React.?
XXXXXXXX	C1 TRT D5	30 mg/m ²	Infusion reaction	XXXXX	DDMMYYYY (XX) HH:MM	No		Infusion reaction	XXXXX	Yes
XXXXXXXX	C2 TRT D2	[D2] mg/m ²	Technical problem	XXXXX	DDMMYYYY (XX) HH:MM	Yes	HH:MM		XXXXX	No

<cont>

Inf.: Infusion; Inter.: Interrupted; Rest.: Restarted; React.: Reaction.

Program: (Program name.sas) (run on: DDMMYYYY HH:MM)

Filename: (Specify file name.rtf)

PROGRAMMING NOTES:

- Listing to be sorted by increasing CPX-POM dose.

Listing 16.2.1-1.1 - Preface to Inclusion and Exclusion Criteria

Protocol Version	Inclusion/Exclusion No.	Inclusion / Exclusion Text

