Center/ Patient	Country	CPX-POM Dose group	Date (day) of Discontinuation/ Completion	Reason for Discontinuation	Date (day) of Last Dose	Date (day) of Death	Reason
XXXX	XXX	30 mg/m ²	DDMMYYYY (XXX)		DDMMYYYY (XXX)		
XXXX	XXX	[D2] mg/m ²	DDMMYYYY (XXX)		DDMMYYYY (XXX)		
XXXX	XXX	[D3] mg/m ²	DDMMYYYY (XXX)		DDMMYYYY (XXX)		
XXXX	XXX	[D4] mg/m ²	DDMMYYYY (XXX)		DDMMYYYY (XXX)		
XXXX	XXX	[D4] mg/m ²	DDMMYYYY (XXX)	Adverse Event	DDMMYYYY (XXX)		
XXXX	XXX	[D4] mg/m ²	DDMMYYYY (XXX)		DDMMYYYY (XXX)		

<etc>

Day was from the date of first dose of CPX-POM administration. Dates are displayed as DDMMYYYY, -- represents an unknown date component.

Program: (Program name.sas) (run on: DDMMYYYY HH:MM)

Filename: (Specify file name.rtf)

Sponsor: CicloMed
Protocol: CPX-POM-001
Statistical Analysis Plan
(TFL shells):
Version 1.0 / 02FEB2018

Protocol: CPX-POM-001

--- DELIVERY TYPE ---

Page 1 of X

Listing 16.2.2 - Protocol Deviations
 (All Patients)

Center/ Patient	CPX-POM Dose group	Category	Details	Leading to Exclusion from Analysis Population?	Analysis Population(s)
XXXX	[D4] mg/m ²	Compliance	Not treated	Yes	SAFETY

<to be completed with the other patients having at least one protocol deviation>

Program: (Program name.sas) (run on: DDMMYYYY HH:MM)

Filename: (Specify file name.rtf)

PROGRAMMING NOTES:

- Listing to be sorted by increasing CPX-POM dose.

Listing 16.2.3-1 - Demographic and Baseline Characteristics
 (All Patients)

Center/ Patient	Country	CPX-POM Dose group	Date of Birth	Age (year)	Sex	Race	Weight (kg)	Height (cm)	BMI (kg/m ²)	BSA (kgxm)	Patient of Child Bearing Potential?	Creat. Clear. (unit)
XXXX	XXX	30 mg/m ²	DDMMYYYY	XX	Male	XXXXX	XXX.X	XXX	XX.X	XX.X		XXX
XXXX	XXX	[D2] mg/m ²	DDMMYYYY	XX	Female	XXXXX	XXX.X	XXX	XX.X	XX.X	Yes	XXX
XXXX	XXX	[D3] mg/m ²	DDMMYYYY	XX	Female	XXXXX	XXX.X	XXX	XX.X	XX.X	No	XXX
XXXX	XXX	[D4] mg/m ²	DDMMYYYY	XX	Male	XXXXX	XXX.X	XXX	XX.X	XX.X		XXX
XXXX	XXX	[D4] mg/m ²	DDMMYYYY	XX	Male	XXXXX	XXX.X	XXX	XX.X	XX.X		XXX
XXXX	XXX	[D4] mg/m ²	DDMMYYYY	XX	Female	XXXXX	XXX.X	XXX	XX.X	XX.X	No	XXX

<etc>

Creat. Clear.: Creatinine Clearance.

Dates are displayed as DDMMYYYY, -- represents an unknown date component. Age was calculated from date of birth and date of screening. BMI (kg/m²) = Weight (kg) / (Height (m))². BSA (kgxm) = 0.007184 x Weight (kg)^{0.425} / (Height (m))^{0.725} (Dubois formula).

Program: (Program name.sas) (run on: DDMMYYYY HH:MM)

Filename: (Specify file name.rtf)

PROGRAMMING NOTES:

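### SAP exposure in mg multiplies the daily dose by the first-to-last-dose calendar span, overstating cumulative dose 2.6-fold at two cycles; separately, the SAP's BSA footnote divides by height

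*SAP*

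**What the plan says.** SAP Table 14.1-7 (Overall Exposure to Study Drug and Drug Compliance) has two exposure rows. Footnote [a] defines exposure in days as "the number of days between the first dose taken date and the last dose taken date + 1 day". Footnote [b] builds on it: "The CPX-POM exposure expressed in mg is defined as: dose per m² x Body Surface Area x CPX-POM exposure expressed in days". Listing 16.2.5 (Drug Exposure) repeats both definitions.

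The schedule is in protocol section 6.1.4: "CPX-POM will be administered as an IV infusion once daily on Days 1-5 of each 21-day treatment cycle". Protocol section 4.2 (Tables 3 and 4) shows that the dose per m² is a daily dose. Section 4.1 lets patients continue for an open-ended number of cycles.

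For BSA, footnote [d] of SAP Table 14.1-3 reads "Body Surface Area (BSA) (kgxm) = 0.007184 x Weight (kg)^{0.425} / (Height (m))^{0.725" (closing brace cut off here) and calls this the Dubois formula. Listing 16.2.3-1 repeats it with the same kgxm unit. Protocol section 6.1.4 gives the Dubois formula as a product, with the height term multiplied in. The BSA used for dosing is a site calculation: "BSA will be calculated by the site personnel using the Dubois method of calculation using screening height and baseline weight measurements" (protocol Table 1, note 23).

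**The concern.** A daily dose has to be multiplied by the number of days on which drug was given. The SAP multiplies it by a calendar span that includes the treatment-free part of every cycle except the last. Any patient treated beyond Cycle 1 would be reported as having received drug that was never given. A dose missed between the first and the last would also count as given.

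The error is not a constant factor. It grows with the number of cycles and with delays between them, so it differs between patients and between dose groups. A reader comparing cumulative dose across cohorts in a first-in-human study could see the order reversed.

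The BSA footnote is a second, independent error. As written, it makes the BSA rows of Table 14.1-3 and the BSA column of Listing 16.2.3-1 wrong. It carries into exposure in mg only if the programmer derives BSA from that footnote instead of using the site's value.

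**Working it through.** The documents print no exposure figure, so there is none to reproduce. The check applies the SAP rules to the protocol schedule.

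**Span error.** For K complete cycles on schedule, the first dose is on study day 1 and the last on day 21(K−1)+5.

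- SAP exposure in days = 21(K−1)+5
- Infusions given = 5K
- Overstatement of mg = [21(K−1)+5] / (5K), with dose and BSA constant and correct

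| Cycles | SAP days | Infusions | Ratio |
|---|---|---|---|
| 1 | 5 | 5 | 1.0 |
| 2 | 26 | 10 | 2.6 |
| 3 | 47 | 15 | 3.13 |
| 4 | 68 | 20 | 3.4 |
| limit | | | 21/5 = 4.2 |

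Two departures from schedule:

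- An assumed 14-day delay before Cycle 2 gives (21+14+5)/10 = 4.0.
- One dose missed in the middle of Cycle 1, with no further cycle, gives 5/4 = 1.25.

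**Effect on ranking.** Assume a 70 kg, 170 cm patient with correctly computed BSA of 1.8097 m², and take two example doses from protocol Table 4.

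- 240 mg/m² for two cycles, given: 240 × 1.8097 × 10 = 4,343 mg
- 240 mg/m² for two cycles, reported: 240 × 1.8097 × 26 = 11,293 mg
- 600 mg/m² for one cycle, given and reported: 600 × 1.8097 × 5 = 5,429 mg

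The true ratio of the first patient to the second is 4,343/5,429 = 0.80. The reported ratio is 11,293/5,429 = 2.08, so the order reverses.

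**BSA error.** The protocol states no units for its formula. Centimetres are assumed because the SAP summarises height in cm, and because metres would give an implausible 0.064 for this patient.

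- Protocol: 0.007184 × W^0.425 × H(cm)^0.725
- SAP: 0.007184 × W^0.425 / H(m)^0.725
- Ratio = H(cm)^0.725 × H(m)^0.725, so weight cancels

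| Weight, height | Protocol | SAP | Ratio |
|---|---|---|---|
| 50 kg, 155 cm | 1.467 | 0.0276 | 53.2 |
| 70 kg, 170 cm | 1.810 | 0.0297 | 60.8 |
| 110 kg, 190 cm | 2.377 | 0.0333 | 71.5 |

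Both Table 14.1-3 (mean and median) and Listing 16.2.3-1 show BSA to one decimal, so these values would print as 0.0.

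**Both errors together.** If BSA were also programmed from the footnote, the 240 mg/m² two-cycle patient would be reported at 240 × 0.02975 × 26 = 186 mg, against 4,343 mg given. The 2.6-fold figure therefore describes the span error alone.

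**The case against.** The main points on the other side are these.

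- **Reach.** Protocol section 9.5.2 defines extent of exposure through plasma and urine levels, so cumulative mg is an addition in the shells. DLT, MTD and adverse-event summaries are by dose group and do not use it. This stands and limits the harm to one table row group and one listing column, plus the BSA outputs.
- **Only the shells are public.** Listing 16.2.8-5 refers to a SAP for further detail. Text not seen here may say which dose and BSA apply and how partial infusions are handled, so those silences carry little weight. The span-times-dose rule is an explicit statement, made twice, and does not depend on unseen text.
- **Direction.** The overstatement assumes a correct BSA. Applying all the footnotes literally gives a large understatement instead. That is true, but neither result is the dose given.
- **Schedule and examples.** The protocol allows for adding five dosing days per cycle. The two-cycle ratio would then be about 1.55 to 1.65, depending on where the days fall. The Table 4 doses are examples, and cycles per patient are not forecast. The ratios are therefore conditional, though under either schedule two full cycles are overstated.
- **Detectability.** A BSA of 0.0 would be noticed, and infusions can be counted from Listing 16.1.7-1. The inflated mg values have no such giveaway, and a reader should not have to rebuild the exposure table from a listing.

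**Conclusion.** Both errors hold as written. The mg rule overstates cumulative dose for any patient treated past Cycle 1: 2.6-fold at two on-schedule cycles, 3.13-fold at three, 3.4-fold at four, with a limit of 4.2. These figures assume five daily infusions per 21-day cycle, no missed doses, and constant dose and correct BSA. There is no error for a single uninterrupted cycle.

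The BSA footnote gives values about 53 to 71 times too small for heights of 155 to 190 cm, assuming the protocol formula takes height in cm.

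The consequence is false exposure and BSA displays, with no effect on dose-escalation decisions or the toxicity analyses. It should be fixed before these outputs are programmed.

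**What to change.** 1. In Table 14.1-7 footnote [b] and Listing 16.2.5, define cumulative dose in mg as the sum, over infusions actually given, of administered dose per m² × the BSA used for dosing in that cycle × the fraction of bag volume infused. At minimum, replace calendar days with the number of infusions given.
2. Keep the first-to-last-dose span, labelled as duration of treatment.
3. In Table 14.1-3 and Listing 16.2.3-1, correct BSA to 0.007184 × weight (kg)^0.425 × height (cm)^0.725, in m².
4. State that exposure in mg uses the site-calculated dosing BSA.

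The cost is small: footnote and derivation changes in two tables and two listings. Bag volume and volume infused are already in Listing 16.1.7-1. The dose level after an adjustment and the per-cycle BSA are not shown there. The dose level must come from the dosing records; BSA can come from the same records or be derived from the weight and height already collected. The minimum version in step 1 needs only a count of infusions.
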